2. LIST OF ABBREVIATIONS

Term	Definition / description
ADME	Absorption, Distribution, Metabolism and Excretion
ALT	Alanine aminotransferase
AST	Aspartate aminotransferase
AUC _{0-∞}	Area under the concentration-time curve of the analyte in plasma over the time interval from 0 extrapolated to infinity
AUC _{0-tz}	Area under the concentration-time curve of the analyte in plasma over the time interval from 0 to the last quantifiable data point
BI	Boehringer Ingelheim
C _{max}	Maximum measured concentration of the analyte in plasma
CV	Arithmetic coefficient of variation
gCV	geometric coefficient of variation
gMean	Geometric mean
ICH	International Council for Harmonisation
PKS	Pharmacokinetic parameter analysis set
RAGe	Report appendix generator
SD	Standard Deviation
t _{max}	Time from (last) dosing to the maximum measured concentration of the analyte in plasma
TS	Treated set
ULN	Upper limit of normal range

3. INTRODUCTION

As per ICH E9 (1), the purpose of this document is to provide a more technical and detailed elaboration of the principal features of the analysis described in the revised CTP and to include detailed procedures for executing the statistical analysis of the primary and secondary variables and other data.

This TSAP assumes familiarity with the CTP and its amendments. In particular, the TSAP is based on the planned analysis specification as written in CTP Section 7 'Statistical Methods and Determination of Sample Size'. Therefore, TSAP readers may consult the revised CTP for more background information on the study, e.g., on study objectives, study design and population, treatments, definition of measurements and variables, planning of sample size, randomisation.

Study data will be stored in a trial database within the RAVE EDC system.

The statistical analyses will be performed within the validated working environment CARE, including SASTM (current Version 9.4 or higher, by [REDACTED]), and a number of SASTM-based tools (e.g., macros for the analyses of AE data or laboratory data; Report Appendix Generator system (RAGe) for compilation/formatting of the CTR appendices).

The trial is kept on-hold. Clinical activities will only re-start after a new benefit-risk assessment has been approved by authorities.

Part A of this trial has been terminated after 12 subjects due to procoagulant effects that interfered also with alteplase analytics. The PK-data could not be used for hypothesis testing and hence the data was only analysed descriptively.

After implementation of measures to mitigate the risk of thromboembolic complications and to avoid methodological problems with alteplase analytics Part B will be performed following a 2-stage design.

The establishment of bioequivalence will be only based on data of Part B (stage 1 and 2).

4. CHANGES IN THE PLANNED ANALYSIS OF THE STUDY

All analyses described in this TSAP are in accordance with the statistical methods planned in the CTP.

5. ENDPOINTS

5.1 PRIMARY ENDPOINT

[figure not shown]
The following pharmacokinetic parameters will be determined for TPA-02 and TPA-05:

[figure not shown]
- *AUC_{0-t_z} (area under the concentration-time curve of the analyte in plasma over the time interval from 0 to the last quantifiable data point)*
- *C_{max} (maximum measured concentration of the analyte in plasma)*

5.2 SECONDARY ENDPOINTS

The following pharmacokinetic parameter will be determined for TPA-02 and TPA-05:

- *AUC_{0-∞} (area under the concentration-time curve of the analyte in plasma over the time interval from 0 extrapolated to infinity)(AUC0-inf_pred and supportive AUC0-inf_obs)*

6. GENERAL ANALYSIS DEFINITIONS

6.1 TREATMENTS

For basic study information on treatments to be administered, assignment of treatment groups, and selection of doses, cf. Section 4 of the CTP.

All subjects will receive the 2 treatments (TPA-02 and TPA-05) in randomised order at 2 consecutive days. The specific alteplase dose to be administered to a given subject will be calculated based on the body weight measured at screening examination. Prior to the first administration of trial medication, subjects will be assigned to treatment sequences T-R or R-T.

For statistical analysis of AEs, safety laboratory data, vital signs and ECG, the following analysis phases are defined for each subject:

Table 6.1: 1 Flow chart of analysis phases for statistical analyses of AEs, safety laboratory and vital signs

Study analysis phase	Label	Start (inclusive)	End (exclusive)
Screening	Screening	Date of informed consent	Date/time of first administration of TPA-02/ TPA-05
On-treatment	TPA-02 0.2 mg/kg body weight	Date/time of first administration of TPA-02	Date/time of first administration of TPA-05 or 12:00 a.m. on day after subject's trial termination date, whichever occurs earlier
On-treatment	TPA-05 0.2 mg/kg body weight	Date/time of first administration of TPA-05	Date/time of first administration of TPA-02 or 12:00 a.m. on day after subject's trial termination date, whichever occurs earlier

Analysis phases for statistical analysis of AEs are defined for each subject as described in the table above.

CTR Section 15, Appendix 16.1.13.1.8.2 and Appendix 16.1.13.1.8.3 AE displays will present results for the on-treatment phase and screening phase.

In CTR Section 15 AE tables (but not in Appendix 16.1.13.1.8.2 and Appendix 16.1.13.1.8.3 AE tables), the following totals will be provided in addition:

- **"Total on-trt"**, defined as the total over all on-treatment phases involving BI

Safety laboratory data and vital signs will be analysed by treatment (TPA-02 or TPA-05).

More details on the technical implementation of these analyses are provided in the ADS Plan of this TSAP.

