Test product	alteplase, TPA-05 (50 mg vial)
dose	0.2 mg/kg body weight
mode of admin.	iv-infusion over 30 min

Proprietary confidential information © 2021 Boehringer Ingelheim International GmbH or one or more of its affiliated companies

Reference product	alteplase, TPA-02 (50 mg vial)
dose	0.2 mg/kg body weight
mode of admin.	iv-infusion over 30 min
Auxiliary medicinal product	Heparin-Natrium-5000-ratiopharm® (unfractionated heparin)
dose	5000 IU
mode of admin.	iv-bolus (5 min prior to start of each alteplase infusion)
Duration of treatment	single dose for each treatment
Statistical methods	
Part A:
 
Only descriptive analyses are performed since the generated PK-data that cannot be used for the confirmatory bioequivalence assessment.
 
Part B:
 
The study design is an adaptive two-stage group-sequential design allowing for unblinded sample size re-estimation after stage 1. The assessment of bioequivalence will be based upon 2-sided repeated confidence intervals (CIs) for the ratios of geometric means (test/reference) for the primary endpoints using an acceptance range of 80.00 to 125.00%. The alpha level for stage 1 is fixed to 0.03585 and a user-defined alpha spending function will be used such that the full level of 0.05 is spent at the final analysis. The final analysis will be performed according to the inverse normal approach.
 
The statistical model for each stage of the trial will be an analysis of variance (ANOVA) on the logarithmic scale including effects for sequence, subjects nested within sequences, period and treatment. p-values will be calculated based on the residual error from the ANOVA and the t-distribution.
 
Descriptive statistics will be calculated for all endpoints.

Proprietary confidential information © 2021 Boehringer Ingelheim International GmbH or one or more of its affiliated companies

FLOW CHART

Trial period	Visit	Day	Planned time (relative to start of infusion [h:min])	Approximate clock time of actual day [h:min]	Event and comment	Safety laboratory	Alteplase Infusion	PK blood (x) / ADA (y)	Biomarkers ⁸	Vital signs (BP, PR)	Questioning for AEs and concomitant therapy ⁶
SCR	1	-21 to -1			Screening (SCR) ¹	A				x	
	2	-1	-12:00	20:00	Admission to site, check of restrictions	x ⁵				x	
		1	-1:30	06:30	Allocation to treatment ²			x ²	x ^{2,8}	x ²	x ²
			-0:15	07:45		B		x,y	x ^{8,9}		
			-0:05	07:55	i.v.-bolus of standard heparin						
			0:00	08:00	Start of alteplase infusion		▲				

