1.5.3.2 Risk associated to heparin administration

Heparin has been tested in several clinical trials with healthy subjects.

Swan et al investigated the safety and anticoagulant effects of argatroban and heparin in two randomised, parallel group dose escalation studies. In the first study 18 subjects received escalating single doses of up to 240 IU/kg (N=3) / 120 IU/kg (N=15) as iv-bolus. In the second study i.v. infusion of heparin at escalating dosage levels (up to 0.30 IU/kg/min) over 4 h with (N=9) and without (N=9) a loading bolus of 125 IU/kg. The most common adverse events in the heparin treated subjects were headache (11.1%), pain at the injection/infusion site (8.3%) and dizziness (5.6%). These adverse events were of mild to moderate severity and resolved spontaneously. Beyond one case of nose bleed (minor) and one case of bruising at the injection/ infusion site no further bleeding events were reported for the heparin group [[R20-4203](#)].

In a drug-drug interaction study, conducted by Teng et al, 28 healthy subjects received a single dose of 180 mg ticagrelor alone, unfractionated heparin 100 IU/kg as iv-bolus alone and both drugs together in a tree period cross-over design. Study treatments were well tolerated by all subjects. No significant bleeding related events occurred. Drug related adverse events were reported for 2 (ticagrelor alone), 2 (heparin alone) and 3 (ticagrelor + heparin) subjects. No clinically relevant changes in 12-lead ECG, vital signs, urinalysis and physical findings were observed [[R20-4204](#)].

According to Gretler et al the combined administration of the GPIIb-IIIa receptor antagonist eptifibatide (180µg/kg bolus followed by 2 µg/kg/min for 48 h) and unfractionated heparin (iv bolus of 5000 IU followed by an infusion of 1000 IU/h adjusted to maintain aPTT

Proprietary confidential information © 2021 Boehringer Ingelheim International GmbH or one or more of its affiliated companies

between 50-70 seconds) was well tolerated by healthy subjects with the exception of one subject. In this case study drug administration was discontinued due to treatment related thrombocytopenia [\[R20-4202\]](#)

Pernerstorfer et al describe the administration of 10.000 IU heparin as iv-bolus to healthy subjects followed by an initial infusion rate of 1000 IU/h (titrated at 3 h and 12 h to keep an aPTT ratio of 2.0 - 2.5 over 24 h. Statements on tolerability have not been made in this publication [\[R20-4200\]](#).

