3.3.4 Withdrawal of subjects from treatment or assessments

Subjects may discontinue trial treatment or withdraw consent to trial participation as a whole ('withdrawal of consent') with very different implications; please see sections [3.3.4.1](#) and [3.3.4.2](#) below.

If a subject is removed from or withdraws from the trial prior to the first administration of trial medication, the data of this subject will not be entered in the case report form (CRF) and will not be reported in the clinical trial report (CTR). If a subject is removed from or withdraws from the trial after the first administration of trial medication, this will be documented and the reason for discontinuation must be recorded in the CRF; in addition, the data will be included in the CRF and will be reported in the CTR. At the time of discontinuation, a complete end of trial examination will be performed, if possible, and the information will be recorded in the CRF. If the discontinuation occurs before the end of the REP (see Section [1.2.3](#)), the discontinued subject should be questioned for AEs and concomitant therapies at or after the end of the REP in order to ensure collection of AEs and concomitant therapies throughout the REP, if not contrary to any consent withdrawal of the subject.

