4 TREATMENTS

4.1 INVESTIGATIONAL TREATMENTS

4.1.1 Identity of the Investigational Medicinal Products

The characteristics of the test product are given below:

Substance: alteplase (from modified manufacturing process: TPA-05)
Protein content: 51.5 mg/vial (Reference: Certificate of Analysis)
Pharmaceutical formulation: Powder and Solvent for Solution for Injection/Infusion
Source: BI Pharma GmbH & Co. KG, Germany
Unit strength: 50 mg powder and 50 ml solvent
Posology: 1-0-0 (0.2 mg/kg body weight)
Route of administration: i.v.
Duration of use: infusion over 30 min (single dose)

The characteristics of the reference product are given below:

Substance: alteplase (from current manufacturing process: TPA-02)
Protein Content: 50.1 mg/vial (Reference: Certificate of Analysis)
Pharmaceutical formulation: Powder and Solvent for Solution for Injection/Infusion
Source: BI Pharma GmbH & Co. KG, Germany
Unit strength: 50 mg powder and 50 ml solvent
Posology: 1-0-0 (0.2 mg/kg body weight)
Route of administration: i.v.
Duration of use: infusion over 30 min (single dose)

Sterile water for Injection/Infusion is used as solvent for both alteplase products. Alteplase (TPA-02 and TPA-05) solution for injection/infusion will be prepared within 30 min prior to its intended use. A detailed reconstitution instruction is given in [Appendix 10.1](#).

Alteplase will be administered as short infusion using a syringe infusion pump (Perfusor fm[®] [REDACTED]). For intravenous drug administration and PK sampling two different intravenous cannulas will be used. They must not be on the same arm during the drug administration.

Proprietary confidential information © 2021 Boehringer Ingelheim International GmbH or one or more of its affiliated companies

The characteristics of the Auxiliary medicinal product are given below:

Drug product: Heparin-Natrium-5000-ratiopharm® (Ampullen)

Pharmaceutical formulation: vial containing solution for injection

Source: [REDACTED]

Unit strength: 0.2 ml (= 5000 IU Heparin-sodium)

Posology: 1-0-0

Route of administration: i.v.

Duration of use: bolus injection (5 min prior to start of each alteplase infusion)

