6.6 HANDLING OF MISSING DATA AND OUTLIERS

Data of screened subjects who were withdrawn from the trial prior to first administration of any study drug will not be reported in the CTR.

Data of subjects who failed to complete all periods of the study (dropouts or withdrawals) will be reported in the CTR as far as their data are available. All withdrawals will be documented and the reason for withdrawal reported in the CTR.

CTP Section 7.5.1: *It is not planned to impute missing values for safety parameters.*

One exception where imputation might be necessary for safety evaluation are AE dates. Missing or incomplete AE dates are imputed according to BI standards (3).

Missing data and outliers of PK data are handled according to BI standards (4) and (5).

CTP Section 7.5.2: *PK parameters that cannot be reasonably calculated based on the available drug concentration-time data will not be imputed.*

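### In Part B, an adverse event that starts between the heparin bolus and the alteplase infusion is tabulated as screening in period 1 and under the previous day's product in period 2

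*SAP*

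**What the plan says.** **Heparin timing.** The protocol synopsis lists heparin 5000 IU as an "iv-bolus (5 min prior to start of each alteplase infusion". Protocol 4.1.1 repeats the timing, and the Flow Chart puts the bolus at 07:55 and the infusion at 08:00 on both treatment days. Protocol 1.5.3.1 and 1.5.3.3 describe the bolus as a Part B measure. Section 4.1.1 introduces heparin separately from test and reference: "The characteristics of the Auxiliary medicinal product are given below".

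**Analysis phases.** In SAP Table 6.1: 1 screening ends, exclusive, at "Date/time of first administration of TPA-02/ TPA-05". The TPA-02 phase ends at "Date/time of first administration of TPA-05 or 12:00 a.m. on day after subject's trial termination date, whichever occurs earlier", and the TPA-05 phase is defined the same way with the products exchanged. SAP 7.8.1 sends every adverse event either to screening or to one of these phases. The SAP text is adapted to Parts A and B but does not mention heparin.

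**Who is reported.** Protocol 3.3.4 keeps data out of the CRF and the trial report "If a subject is removed from or withdraws from the trial prior to the first administration of trial medication". SAP 6.6 says that data of screened subjects "withdrawn from the trial prior to first administration of any study drug will not be reported in the CTR". SAP 6.3, taken from protocol 7.3, requires at least one dose of study drug for the treated set (TS-B).

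**The concern.** The phase boundary is tied to the second of two drugs given in sequence. Protocol 1.3 says that intravenous heparin acts at once, and it lists allergic reactions, anaphylactic shock among them. A reaction in the minutes after the bolus is therefore plausible, and the current table cannot place it in the period in which it happened.

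At stake is the tabulation of reactions to a product that was added to Part B as a safety measure. In period 1 such an event drops out of 'Total on-trt'. In period 2 it appears in the column of the alteplase product from the day before. If the subject never goes on to alteplase, he may not enter the safety set at all.

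**Working it through.** There is no figure in the plan to reproduce. The check applies the table's start (inclusive) and end (exclusive) rules to the Flow Chart times.

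**Inputs.** Bolus at 07:55 and alteplase at 08:00 on two consecutive days (Flow Chart). Infusion starts at least 24 h apart (protocol 6.2.2), taken here as exactly 24 h. Residual effect period 24 h (protocol 1.2.6; SAP 7.8.1).

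**Phase assignment.**

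| Onset | Hours from first alteplase start | Phase under Table 6.1: 1 | Phase if it opened at the bolus |
|---|---|---|---|
| Period 1, 07:55 | −5/60 = −0.083 | Screening | Period-1 product |
| Period 1, 08:00 | 0 | Period-1 product | Period-1 product |
| Period 2, 07:55 | 24 − 5/60 = 23.917 | Period-1 product | Period-2 product |
| Period 2, 08:00 | 24 | Period-2 product | Period-2 product |

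Only onsets from 07:55 to just before 08:00 change. A gap longer than 24 h does not alter the SAP result, because the first product's phase runs until the second alteplase product starts.

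**Does the protocol correct this?** No. Protocol 7.3.4 assigns events before the first intake of trial medication to screening and events up to the end of the residual effect period to the treatment. At 23.92 to <24.00 h the period-2 window lies inside the 24 h of dose 1, so the protocol gives the same product. If the gap exceeds 24 h, the protocol calls the interval follow-up but still summarises it under the previous treatment.

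**Exposure to the rule.** Each subject dosed in both periods has one window of each kind. Stage 1: 18 + 18 = 36 windows. Maximum Part B (18 + 42 = 60 subjects): 60 + 60 = 120 windows. Each lasts 5 minutes.

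**The subject who never receives alteplase.** Set side by side:

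- Protocol 3.3.4 turns on trial medication, SAP 6.6 on any study drug, and the treated set on study drug. None says whether heparin counts.
- Protocol 4.3 uses trial medication for the substance measured in plasma, which points to alteplase only. Protocol 4.1.1 places heparin within the section on investigational treatments, which points the other way.
- Protocol 5.2.6.2.1 collects adverse events from consent onwards and exempts from CRF entry only screening failures before any trial medication. A randomised subject who reacts to the bolus is not obviously a screening failure, so this exemption is narrower than the rule in 3.3.4.

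If the terms mean alteplase only, protocol 3.3.4 keeps this subject out of the CRF and the trial report, and SAP 6.3 keeps him out of TS-B. If they include heparin, he is in all three.

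**The case against.** **No event count.** The protocol cites, for heparin-treated healthy subjects, "pain at the injection/infusion site (8.3"%). A reader might multiply this by the boluses: 0.083 × 36 = 3.0 and 0.083 × 120 = 10.0 misassigned events. The documents do not support that. The rate is per subject, whereas SAP 7.8.1 counts subjects with events; per subject the products would be 0.083 × 18 = 1.5 and 0.083 × 60 = 5.0. It also comes from dose-escalation studies with boluses up to 240 IU/kg and 4-hour infusions. Here the bolus is 5000/100 = 50 to 5000/65 = 77 IU/kg. Nothing says what share of events starts within 5 minutes. This objection stands in full.

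**Serious reactions would not be lost.** A reader might infer that an anaphylactic reaction could go unnoticed. Protocol 5.2.6.2.2 requires serious and special-interest events to reach the sponsor within 24 hours, and SAP 6.1 displays screening-phase events if the subject goes on to alteplase. The reporting gap is confined to the CRF and the trial report, and to the alteplase-only reading.

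**No bias between products.** A reader might infer that the TPA-05 versus TPA-02 safety comparison is distorted. Heparin is the same before both products and sequences are allocated 1:1, so period-2 shifts are expected to balance (9 windows charged to each product in stage 1). That removes systematic bias. It does not put a single event in the right column, and it does not restore period-1 events to the on-treatment total.

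**Another convention.** Starting the phase at the bolus would list under an alteplase product some reactions that it cannot have caused. That is fair, and is why a separate heparin interval is offered below.

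**Conclusion.** The point holds as a minor defect of definition. By the table's own rules, a Part B event starting between bolus and infusion is tabulated as screening in period 1 and under the other product in period 2. This rests only on the scheduled order of bolus and infusion. The further consequence, absence from TS-B and the trial report, is conditional on heparin not being study drug or trial medication, which the documents leave open.

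The size is one 5-minute window per period. Safety analysis is descriptive, the bioequivalence test is untouched, Part A is not concerned, and the number of affected events cannot be estimated from the documents. The ADS plan that SAP 6.1 cites for technical detail was not available, but the table is explicit. It is worth changing because the rule misplaces events and correcting it is cheap.

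**What to change.** For Part B only:

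1. In SAP Table 6.1: 1, end the preceding phase at the actual date and time of that period's heparin bolus. Then either start that period's on-treatment phase there, or define a heparin interval from bolus to infusion start and include it in 'Total on-trt'. Protocol 7.3.4 already allows further intervals in the SAP.
2. State in SAP 6.3 and 6.6 that a randomised subject given the bolus belongs to the safety set and is reported. Align protocol 3.3.4 and 7.3 with this, and reconcile 3.3.4 with the narrower exemption in 5.2.6.2.1.
3. Confirm that actual bolus times are recorded. Protocol 4.1.4 requires this expressly for the start and end of the infusion; the text shows no equivalent for the bolus.

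Part A phases stay as they are.

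**Cost.** One changed boundary, a short statement on the safety set, and matching protocol wording. The only possible new data item is the bolus time. Scheduled pre-dose assessments fall at −1:30 and −0:15, before the bolus, so scheduled baselines do not move. If the on-treatment phase simply starts at the bolus, some reactions that alteplase cannot have caused will be tabulated under that period's regimen; the separate interval avoids this.
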